- ✗ PRO questionnaires (EORTC QLQ-LC13, EORTC QLQ-C30, EORTC IL46, and EQ-5D-5L) will be completed by the participants at the start of the clinic visit before discussion of the participant's health state, laboratory results, or health record; before administration of study treatment; and/or prior to the performance of any other study assessments that could bias the participant's responses. In scenarios where laboratory assessments (e.g., blood draws) are done in a different clinic than the one providing treatment or when they are done on a different day than study treatment administration, laboratory assessments can be completed before the completion of PROs as long as results have not been discussed with the participant. If the participant comes to the clinic for study drug administration, completes the PRO questionnaires and then does not receive study treatment (i.e., a decision is made that study treatment cannot be administered on that day due to the participant's health status), the collected PROs should be kept and questionnaires for this timepoint should not be re-administered on the day of the delayed study drug administration. The questionnaires will be completed on Cycle 1, Day 1 (baseline); Cycle 2, Day 1; Cycle 3, Day 1; Cycle 4, Day 1, and Cycle 5, Day 1. From Cycle 6 onwards, the questionnaires will be completed at every other study treatment cycle prior to the administration of study drug (i.e., on Cycle 6, Day 1; Cycle 8, Day 1; Cycle 10, Day 1; etc.). PROs will be collected during the treatment period and at the study treatment discontinuation visit. During follow-up, PROs (EORTC QLQ-C30, EORTC QLQ-LC13 and EQ-5D-5L) will be completed at 3 months ( $\pm$  30 days) and 6 months ( $\pm$  30 days). The PRO instruments will be self-administered by the participant via ePRO device or may be collected remotely on non-visiting dates (e.g., during follow-up or in exceptional circumstances).

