4.2.2 Main Analytical Approach for Primary Estimands

For IRF-assessed PFS, participants who have not experienced disease progression and have not died by the clinical cutoff date will be censored at the time of the last tumor assessment. Participants who have no tumor assessment after baseline and have not died by the clinical cutoff date will be censored at the date of randomization.

For OS, participants who are not reported as having died by the clinical cutoff date will be censored at the date when they were last known to be alive. Participants who do not have information after baseline will be censored at the date of randomization.

Participants who are lost to follow-up will be censored at the last date they were known to be alive for the primary analysis of OS.

Each of the primary endpoints will be compared between two treatment arms based on the stratified log-rank test. The HR will be estimated with use of a stratified Cox regression model, including two-sided 95% confidence intervals (CIs). The stratification factors will be those used for randomization (as listed in Section 1.2.1). The Kaplan-Meier methodology will be used to estimate the median IRF-assessed PFS and median OS for each treatment arm, and Kaplan-Meier curves will be constructed to provide a

visual description of the difference between treatment arms. The Brookmeyer-Crowley methodology will be used to construct the 95% CIs for the median IRF-assessed PFS and median OS for each treatment arm ([Brookmeyer and Crowley 1982](#)). Results from an unstratified analysis will also be provided.

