4.3.6 Time to Confirmed Deterioration

Confirmed clinically meaningful deterioration for physical functioning and Global Health Status (GHS)/Quality of Life (QoL) is defined as a clinically meaningful decrease from baseline in the physical functioning or GHS/QoL scores that must be held for at least two consecutive assessments or an initial clinically meaningful decrease above baseline followed by death attributable to cancer progression within 6 weeks of the last deteriorated PRO assessment. A score change of \geq 10-point change in GHS/QoL and functional subscale scores is perceived by participants as clinically meaningful (Osoba et al. 1998).

For time to confirmed deterioration (TTCD), data for participants will be censored at the last time when they completed an assessment if they have not experienced a confirmed clinically meaningful deterioration at the clinical cutoff date. If no baseline or post-baseline assessment is performed, participants will be censored at the randomization date. According to the while-on-treatment/while-alive strategy, participants who die before reporting any clinically meaningful deterioration will be censored at the last time they completed an assessment. Time to confirmed deterioration using the European Organization for Research and Treatment of Cancer (EORTC) scale will be analyzed with use of the same methods as for PFS.

[REDACTED]

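### The Kaplan-Meier curves and medians planned for time to confirmed deterioration overstate the while-alive probability of deterioration, because deaths before deterioration are censored

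*SAP*

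**What the plan says.** SAP 1.1, Table 2, lists TTCD in physical functioning and global health status as a secondary endpoint. SAP 4.3.6 sets three rules that matter here:

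- In general, participants are "censored at the last time when they completed an assessment if they have not experienced a confirmed clinically meaningful deterioration".
- For deaths without deterioration: "According to the while-on-treatment/while-alive strategy, participants who die before reporting any clinically meaningful deterioration will be censored" at their last completed assessment.
- Some deaths are events: a first meaningful decrease "followed by death attributable to cancer progression within 6 weeks of the last deteriorated PRO assessment" counts as confirmed deterioration.

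TTCD "will be analyzed with use of the same methods as for PFS". SAP 4.2.2 defines those methods. "Each of the primary endpoints will be compared between two treatment arms based on the stratified log-rank test", a stratified Cox model gives the hazard ratio, and the Kaplan-Meier "methodology will be used to estimate the median IRF-assessed PFS and median OS for each treatment arm", with curves and Brookmeyer-Crowley intervals. The visible TTCD text plans no cumulative incidence or other competing-risk summary.

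On data collection, the PRO footnote to Protocol Table 2 says: "During follow-up, PROs (EORTC QLQ-C30, EORTC QLQ-LC13 and EQ-5D-5L) will be completed at 3 months" and again at 6 months, each within 30 days either way. Nothing in SAP 4.3.6 stops counting at the end of treatment. Type I error control (SAP 2.2.1) covers OS and IRF-assessed PFS only.

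**The concern.** For PFS, death is itself an event, so one minus Kaplan-Meier is the probability of something that happens to participants. For TTCD the same estimator is carried over, but the role of death has changed. A participant who dies without deteriorating leaves the risk set as if later deterioration were still possible. The result describes deterioration in a setting where those deaths do not occur, and even that reading requires death and deterioration to be independent. A while-alive question asks what proportion deteriorate before dying, and that needs death treated as a competing event.

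The label also joins two strategies. While-on-treatment would discard the 3- and 6-month follow-up questionnaires; while-alive keeps them, and so does the censoring rule.

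TTCD carries the secondary quality-of-life objective, and readers will take its medians and curves as what participants lived through. OS is planned to differ between arms, so the distortion need not cancel in the comparison.

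**Working it through.** **What the plan gives.** No TTCD event rate, median, event count or power is stated, so there is no TTCD figure to reproduce. The death rates below come from the OS design in SAP 2.2.2, which does reproduce. The medians give 12.5/17.6 = 0.710, matching the stated HR of 0.71. With one interim at 219/323 = 0.678 of the information and the stated spending function, the final critical value is z = 2.084. The minimum detectable HR is then exp(−2 × 2.084/√323) = 0.793, as stated, and power at 323 deaths is 85.1%.

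**Assumptions, not in the documents.**
- Constant hazards, with death independent of deterioration.
- Deterioration median, if death did not occur, of 6 to 24 months.
- Share *s* of the planned death hazard that falls before deterioration of 25% to 100%.

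**Formulas.** Let λ = ln 2/(deterioration median) and δ = *s* × ln 2/(OS median).
- Kaplan-Meier with deaths censored: 1 − exp(−λt).
- While-alive cumulative incidence: λ/(λ+δ) × [1 − exp(−(λ+δ)t)].

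**Worked case.** Control arm, 6-month deterioration median, *s* = 50%, t = 12: λ = 0.1155 and δ = 0.5 × 0.0555 = 0.0277. Kaplan-Meier gives 1 − exp(−1.386) = 0.750. Cumulative incidence gives 0.806 × (1 − exp(−1.719)) = 0.662.

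**12-month incidence, 6-month deterioration median in both arms:**

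| Share *s* | Kaplan-Meier, each arm | Cumulative incidence, control | Gap (points) | Cumulative incidence, experimental | Gap (points) |
|---|---|---|---|---|---|
| 25% | 0.750 | 0.704 | 4.6 | 0.717 | 3.3 |
| 50% | 0.750 | 0.662 | 8.8 | 0.686 | 6.4 |
| 100% | 0.750 | 0.589 | 16.1 | 0.630 | 12.0 |

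The deterioration hazards are equal here, so Kaplan-Meier shows no arm difference. The cumulative incidences differ only because the death rates do.

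**Across the control-arm grid.** The 12-month gap runs from 2.2 points (24-month deterioration median, *s* = 25%: 0.293 against 0.271) to 16.1 points.

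**Medians, control arm, for *s* = 25%, 50%, 100%.**
- Kaplan-Meier 6.0 months: half have deteriorated by 6.3, 6.8 or 7.9 months.
- Kaplan-Meier 12.0 months: 13.5, 15.8 or 34.6 months.
- Kaplan-Meier 18 or 24 months with *s* = 100%: cumulative incidence levels off at 0.410 or 0.342, so no median exists although Kaplan-Meier reports one.

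**If death and deterioration are correlated.** A shared gamma frailty was simulated (control arm, 6-month baseline deterioration median, *s* = 100%). With frailty variance 0.5, Kaplan-Meier at 12 months is 0.616, against 0.651 for the no-death quantity and 0.512 for cumulative incidence. With variance 1.0 the figures are 0.528, 0.580 and 0.453. Kaplan-Meier then matches neither target.

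**Hazard ratio.** With equal deterioration hazards, the simulated Cox estimates with deaths censored were 1.01 to 1.06 across scenarios, near the true value of 1.

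**The case against.** Several stronger readings are tempting, and the documents do not support them.

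- *The whole TTCD analysis fails.* It does not. With deaths censored, the log-rank test and Cox model compare the hazard of deterioration among those still alive, which suits a while-alive question. Only the curves and medians are mismatched.
- *All deaths are censored.* They are not. A progression death within 6 weeks of a deteriorated assessment is an event.
- *The double label changes which data count.* It changes no rule. The only operational instruction is to censor at the last completed assessment, with no cut at treatment stop. This is a wording fault.
- *Death before deterioration is known to be common.* The plan gives OS medians, not the rate of death without prior deterioration. At the low end the effect is modest: 75.0% against 70.4%, with a median of 6.0 against 6.3 months.

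Two practical objections stand. First, questionnaires often stop well before death. As an illustration, add the planned PFS median, about 1 month to the discontinuation visit, and 6 months of follow-up: 2.6 + 1 + 6 = 9.6 months in the control arm and 5.2 + 1 + 6 = 12.2 months in the experimental arm. The OS medians are 12.5 and 17.6 months. Counting every later death as a competing event assumes no deterioration in the unobserved interval and would understate incidence. Censoring all such participants removes the competing event. A cumulative incidence analysis therefore needs an explicit rule. Second, the Version 8 rationale in the Protocol says that the cut-off for the final OS analysis has been reached and some analyses are complete. Replacing prespecified output now would be a post hoc change; adding to it is defensible.

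**Conclusion.** The point holds for the Kaplan-Meier curves and medians only. With deaths before deterioration censored, they describe a hypothetical setting and overstate the while-alive probability of deterioration. Under the assumed ranges the control-arm overstatement at 12 months is about 2 to 16 percentage points. For a 6-month deterioration median it is 75% against 70% to 59%. The gap can differ by arm: 16.1 against 12.0 points in the most extreme case shown. All of these sizes depend on assumed deterioration rates, an assumed share of deaths falling before deterioration, and constant hazards. The hazard ratio and test stand as cause-specific. TTCD is secondary and outside alpha control, so no primary conclusion is affected.

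**What to change.** In SAP 4.3.6:

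1. Name one strategy, while-alive, which the censoring rule already implements.
2. Label the stratified hazard ratio as cause-specific.
3. Add Aalen-Johansen cumulative incidence of confirmed deterioration by arm, with death before deterioration as a competing event.
4. Keep the prespecified Kaplan-Meier curves and medians, labelled as hypothetical with deaths censored.
5. State how deaths after the last questionnaire are handled. One option is to count a death as a competing event only if it falls within a set window of the last scheduled PRO assessment and otherwise to censor at the last PRO, with a sensitivity analysis counting all such deaths.

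The cost is SAP wording and one extra analysis on data already collected, including the work of fixing the window in step 5. Because it comes after the final OS cut-off, it should be labelled supplementary. The added curves will be less directly comparable with earlier trials that reported Kaplan-Meier.

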4.4 EXPLORATORY ENDPOINTS ANALYSES

4.4.1 Laboratory data and Vital signs

Selected laboratory data will be graded according to NCI CTCAE v5.0 and will be summarized by treatment arm with shift tables from baseline to worst post baseline value. Changes in vital signs will also be summarized.

[REDACTED]

4.4.4 Clinical Outcome Assessment Analyses

Summary statistics (mean, standard deviation, median, 25th and 75th percentiles, and range) and the mean change from baseline of linear-transformed scores will be reported for all of the items and scales of the EORTC quality of life questionnaire core 30 (QLQ-C30) and EORTC QLQ-LC13 (lung cancer-specific subset) questionnaires according to the EORTC scoring manual guidelines. These will be reported separately for the induction period and the maintenance period, with baseline being defined as Cycle 1 Day1(C1D1) for each period.

Patient-Reported-Outcome-CTCAE (tolerability as measured by severity, frequency and/or interference of relevant events) and EORTC IL46 (a single item for level of bothersome experienced from treatment) analyses will be conducted in the SAS. Analyses will be descriptive (frequency counts and percentages). For the Participant Reported Outcome-common Terminology Criteria for Adverse Events (PRO-CTCAE), there will be a focus on characterizing the pattern of symptomatic treatment toxicities during the study. The EORTC IL46 and PRO-CTCAE data will be summarized at the item level. For each treatment arm, the number and percentage of participants reporting symptom by “frequency”, “severity”, “interference” and “presence” category will be reported at each assessment. A summary table of the percentage of participants reporting severity of a symptom as “severe” or “very severe” over the course of the study by treatment arm will also be provided. Change from baseline of severity for PRO-CTCAE selected items will be summarized separately for the induction and maintenance periods. Finally, a longitudinal analysis of change may be employed to understand how symptoms may have changed over the course of treatment. Results from these exploratory analyses will be presented separately from other safety analyses. EORTC IL46 will be summarized as frequencies by treatment arm and by timepoint. Some of those exploratory analyses might not be included in the Clinical Study Report (CSR).

Completion rates of questionnaires will be summarized at each timepoint by treatment arm.

4.5 OTHER SAFETY ANALYSES

4.5.1 Extent of Exposure

Drug exposure will be summarized during the maintenance phase in the SAS, including duration, dosage, and dose intensity.

Additionally, drug exposure of atezolizumab and chemotherapy during the induction phase will be summarized to include number of doses and dose intensity with use of descriptive statistics for the enrolled SAS.

4.5.2 Adverse events

AEs, serious AEs, and death (cause of death) during the induction phase will be summarized for the enrolled SAS.

4.5.3 Additional Safety Assessments

4.5.3.1 Laboratory Data and Vital Signs

Laboratory data with values outside of the normal ranges will be identified. Vital signs may also be summarized by treatment arm and visit.

4.6 OTHER ANALYSES

[figure not shown]
4.6.1 Summaries of Conduct of Study

Study enrollment, study drug administration, reasons for discontinuation from the study treatment, and reasons for study discontinuation will be summarized for the enrolled analysis set, the enrolled SAS, the FAS, or the SAS by treatment arm as appropriate. Major protocol deviations, including major deviations of inclusion/exclusion criteria, will be reported and summarized for the enrolled analysis set and for the FAS by treatment arm.

4.6.2 Summaries of Demographics and Baseline Characteristics

Demographics (e.g., sex, age) and baseline characteristics (e.g., ECOG Performance Score, LDH) will be summarized for the FAS by treatment arm. Baseline measurements are the last available data obtained prior to the participant receiving the first dose of any component of protocol treatment in the maintenance phase, unless otherwise noted. Descriptive statistics (mean, standard deviation, median and range) will be presented for continuous variables and counts and percentages will be presented for categorical variables.

5. SUPPORTING DOCUMENTATION

This section is not applicable since there is no additional supporting document.

